## 1.0 Study Summary

Study Title	Streamlined Genetic Testing In Prostate Cancer
Study Design	Pilot Randomized Controlled Trial
Primary Objective	To evaluate the impact and efficacy of a streamlined genetic education and testing intervention for men with prostate cancer.
Secondary Objective(s)	
Research Intervention(s)/ Investigational Agent(s)	Streamlined genetic education and testing intervention.
IND/IDE #	n/a
Study Population	Eligible participants are men who are currently being followed at MGUH or MWHC for metastatic prostate cancer or Gleason 7+ prostate cancer with Ashkenazi Jewish ancestry or Gleason 7+ with a family history of breast, ovarian, pancreatic or prostate cancer.
Sample Size	120
Study Duration for individual participants	Three-months.
Study Specific Abbreviations/ Definitions	MGUH: Medstar Georgetown University Hospital; MWHC: Medstar Washington Hospital Center; PV: Pathogenic Variant; VUS: Variant of Uncertain Significance; ST: Streamlined Testing; UC: Usual Care; EMR: Electronic Medical Record; SRBSR: Subject Recruitment and Biospecimen Shared Resource

## 2.0 Objectives\*

Genetic testing is established as part of clinical care for women with breast and ovarian cancer. Clear guidelines have led to increasing genetic testing participation among eligible women. Identifying pathogenic variants (PVs) in cancer susceptibility genes has important treatment, management and risk reduction implications for breast and ovarian cancer patients and their family members. Men are just as likely as women to carry a PV in a cancer risk gene and men with prostate cancer are at particularly high risk for carrying a PV. NCCN guidelines recommend germline genetic testing in all men with metastatic prostate cancer or with Gleason 7+ prostate cancer and Ashkenazi Jewish ancestry or a family history of prostate, breast, ovarian or pancreatic cancer. These guidelines are likely to expand given recent studies suggesting that 17% of prostate cancer patients may harbor a cancer susceptibility PV and that current referral criteria miss many of these patients. Prostate cancer patients with a PV in *BRCA1* or *BRCA2* (*BRCA*) have more aggressive prostate cancers, are at risk for other primary cancers (e.g., male breast and pancreatic) and their family members are at risk for a variety of cancers. Thus, genetic testing of prostate cancer patients has implications for treatment, management, and risk reduction for the patient and his family members.

Despite these benefits and existing referral guidelines, few men with prostate cancer are tested. This reflects low genetic counseling referral and participation, since men who attend genetic counseling get tested at the same high rate as women. Low participation in genetic counseling is likely due to men's underestimation of the personal health relevance of testing and lack of physician genetic counseling referral. Thus, the requirement to obtain individual genetic counseling prior to genetic testing may be a barrier to the receipt of guideline consistent genetic testing. In fact, recent evidence suggests that traditional comprehensive, patient-centered, educationally focused pre-test genetic counseling often does not match the needs of patients. Further, as genetic referral guidelines continue to expand, demand for genetic counseling will outstrip delivery capacity. Thus, alternative approaches that raise awareness and facilitate access to genetic testing are needed to maximize our ability to extend the benefits of testing to prostate cancer patients and their family members while at the same time accommodating increased demand and conserving scarce genetic counseling resources.

In the proposed pilot, we will develop and test a proactive and streamlined pre-test genetic education (ST) print intervention designed to speed, simplify and target genetic testing delivery for prostate cancer patients. Participants randomized to ST will have the option to proceed directly to genetic testing bypassing traditional pre-test genetic counseling. In contrast, usual care (UC) participants will be informed that they meet guidelines for genetic counseling referral and will be provided with contact information to schedule a standard telephone pre-test genetic counseling session. All participants with a PV or variant of uncertain significance (VUS) will be scheduled for a telephone genetic counseling disclosure session. ST participants who are found not to carry a PV or VUS will have this result disclosed via clinical letter while disclosure for all UC participants will be per standard clinical care by the genetic counselor by phone. By proactively identifying eligible patients, providing streamlined information and facilitating genetic testing, the ST intervention will increase awareness, facilitate informed testing decisions, remove the barrier of pre-test genetic counseling and improve genetic testing delivery capacity.

We will enroll eligible prostate patients who were diagnosed between 2010 and 2019 and are being followed within radiation and medical oncology clinics at the MedStar Georgetown University Hospital (MGUH) and MedStar Washington Hospital Center (MWHC). In this initial pilot, we will not focus on newly diagnosed patients but instead will focus on patients who are being followed for a number of reasons: 1) Substantial numbers of patients who are currently being followed have now become candidates for genetic testing based on updated guidelines and 2) This will allow us to maximize our potential sample size within the one year framework of this grant, allowing us to obtain preliminary efficacy data in preparation for a planned multisite R01 study of newly diagnosed patients with high risk localized or metastatic disease. By providing information particularly salient to prostate cancer patients, reducing barriers to genetic testing and proactively facilitating genetic testing delivery, we expect that our proactive and streamlined approach will yield increased uptake of genetic testing. Our specific aims are:

- 1: **Evaluate the impact of ST vs. UC on genetic testing uptake.** *H1.1:* Patients randomized to ST will be more likely to complete genetic testing compared to UC. *H1.2:* Participants randomized to ST will make better informed genetic testing decisions (characterized by high knowledge, risk comprehension and concordance with attitudes) compared to UC. *H1.3:* Few patients in the ST arm will opt for traditional genetic counseling prior to testing.
- 2: **Evaluate patient satisfaction and psychosocial outcomes in ST vs. UC.** *H2.1:* Compared to UC, those randomized to ST will be more satisfied with their genetic testing decision and will have less decisional regret.
- 3: **Evaluate the impact of ST vs. UC on uptake of cascade testing in unaffected family members.** In exploratory analyses designed to provide effect size estimates, we will compare the arms on rates of genetic testing in relatives of patients found to carry a PV.

### 3.0 Background\*

**Germline Genetic Testing in Prostate Cancer.** Up to 17% of men with prostate cancer have an inherited PV in a cancer gene. For many of these men, this knowledge may impact their medical management. Prostate cancer patients with *BRCA* PV develop higher risk disease than non-carriers. Prostate cancer patients with a *BRCA* PV with localized disease have more frequent nodal involvement, higher Gleason scores, more T3/T4 disease and lower cause specific overall survival at 5 years. Men with metastatic castration-resistant prostate cancer have significantly shorter cause specific overall survival in *BRCA2* carriers vs. non-carriers. The use of single agent PARP inhibitors in patients with *BRCA* PVs and metastatic castration-resistant prostate cancer was associated with high rates of response, leading the FDA to grant breakthrough therapy designation for olaparib and rucaparib in patients with *BRCA* positive metastatic castration resistant prostate cancer. NCCN guidelines suggest germline testing in patients with castration resistant metastatic prostate cancer to guide the early use of platinum chemotherapy as well as for eligibility for clinical trials using PARP inhibitors. In addition, prostate cancer patients with localized Gleason Grade 7+ prostate cancer are recommended to consider genetic testing if they have a family history of breast, ovarian, pancreatic or prostate cancer or are of Ashkenazi Jewish ancestry, regardless of family history. All prostate cancer patients with a *BRCA* PV are at increased risk for second malignancy (e.g., pancreatic cancer, male breast cancer, melanoma). The identification of a PV in a prostate cancer patient also has important

implications for his male and female family members who can use test results to guide their cancer risk reduction and management decisions. *Thus, the identification of a PV in a prostate cancer patient may often have treatment and risk management implications for the patient and his unaffected family members.*

**Awareness and Access to Genetic Testing.** Despite clear benefits and established guidelines, few men with prostate cancer get genetic testing. Men underestimate the personal relevance of *BRCA* mutations and have poorer knowledge and awareness of testing. Although physicians are less likely to refer men for genetic counseling than women and genetic education materials are generally not targeted to men, evidence indicates that when provided with adequate information men have increased uptake rates. Finally, emerging evidence also suggests that the requirement for traditional in-person genetic counseling may be a barrier to genetic testing among men. While men and women have comparable rates of genetic testing uptake *after* genetic counseling, men are much less likely to participate in genetic counseling. *Thus, our intervention is designed to increase appropriate uptake of genetic testing by proactively providing relevant genetic information emphasizing the personal and family relevance of testing to prostate cancer survivors while reducing barriers to genetic testing.*

These goals align with recent changes in genetic service delivery. Given rapidly increasing demand for genetic services, genetic counseling capacity has emerged as a rate limiting factor. *This lack of capacity will become more significant as genetic testing expands in cancer and beyond - prompting consideration of alternative delivery approaches that improve access and efficiency.* While studies have generally indicated that traditional genetic counseling results in positive participant outcomes, recent research suggest that the quantity, relevance and complexity of the information provided in genetic counseling does not always match patient needs. This is particularly true in the cancer setting where the issues covered in traditional genetic counseling may not be of primary concern. Further, most patients who meet clinical referral criteria will not be found to carry a PV. Thus, requiring comprehensive pre-test genetic counseling may not meet the needs of patients and survivors, is inefficient and may serve as a barrier to testing.

Given the unsustainability of the entrenched genetic counseling model, alternative strategies must be considered. We are at the forefront of developing practice changing alternatives to traditional genetic service delivery. We were the first to document the impact of rapid presurgical genetic testing for newly diagnosed breast cancer patients and that access to genetic counseling can be safely and effectively expanded via telephone delivery. Both of these approaches are now part of standard care. More recently, we and others have focused on streamlining content and delivery to more effectively address access and demand while removing barriers that patients find overwhelming or irrelevant. An approach labeled 'direct testing' or 'post-test only', provides patients with brief print information prior to testing. This approach has been used in studies of population-based testing and in newly diagnosed breast, ovarian and colorectal cancer patients. A recent single-arm trial of a brief pre-test summary letter for newly diagnosed breast cancer patients yielded high patient satisfaction and only 2% of participants contacted the study genetic counselor with questions. *Although these studies provide promising preliminary data, it is important to note the lack of RCTs and the focus on populations with high rates of testing. We propose an RCT designed to: 1) proactively deliver genetic education to increase awareness and knowledge among patients who underutilize testing; 2) eliminate*

*the pre-test genetic counseling requirement for patients who wish to proceed directly to testing; and 3) direct scarce genetic counseling resources to patients who receive a PV result – the patients most vulnerable to adverse outcomes. This pilot will provide preliminary data supporting a planned R01 for a multisite RCT of ST vs UC in newly diagnosed prostate patients.*

## **4.0 Study Endpoints\***

### **4.1 Primary and secondary endpoints:**

1. Genetic test uptake
2. Receipt of pre-test genetic counseling
3. Psychosocial outcomes (Satisfaction, distress, decision regret)
4. Use of cascade testing among unaffected family members of mutation carriers

## **5.0 Study Intervention/Investigational Agent**

The streamlined testing (ST) intervention includes: proactive identification and contact of patients eligible for genetic services, streamlined pre-test genetic education, facilitated delivery of genetic testing, targeted genetic counseling disclosure for patients with a PV or variant of uncertain clinical significance (VUS) and a clinical disclosure letter for patients who do not carry a PV. We have developed a range of media for cancer risk communication, including print, electronic and in-person education. The ST print materials will include the following topics: 1) Introduction and explanation of genetic testing guidelines for prostate cancer patients; 2) Explanation of panel testing and potential genetic testing outcomes (positive, negative, uncertain variant); 3) Personal implications of a PV (cancer risks associated with a positive genetic testing result; treatment/management, risk management for second cancers); 4) Implications for family members; 5) Legislation to protect against genetic discrimination; 6) Process of genetic testing: DNA collection (saliva kit), costs, and insurance coverage; 7) Options for and logistics of genetic counseling: pre-test counseling is optional unless required by insurance; post-test genetic counseling for all positives (no charge for telephone genetic counseling). Drawing on our prior work, the ST materials will include text, images, illustrations and graphics. We expect that the material will take 10-15 minutes to review. *Participants randomized to the usual care (UC) arm will be sent a letter from their physician indicating that they meet eligibility criteria for genetic counseling and recommending that they schedule genetic counseling. UC participants can receive free telephone genetic counseling through the study.*

## **6.0 Procedures Involved\***

6.1-6.4 The objective is to develop and pilot a novel streamlined approach to deliver genetic education and testing to the rapidly increasing number of prostate cancer patients who meet guidelines for genetic referral. Our streamlined genetic testing approach is designed to facilitate genetic education and testing for men with prostate cancer. The intervention will incorporate proactively delivered print educational materials in lieu of pre-test genetic counseling. The materials will increase awareness, expand access, provide

balanced information to foster informed genetic testing decisions and reduce barriers to facilitate the delivery of genetic testing. All men who are found to carry a PV or variant of uncertain significance (VUS) in a cancer risk gene will have an individual telephone genetic counseling disclosure session with a board-certified genetic counselor. We will recruit 120 prostate cancer survivors who meet clinical referral criteria. After a baseline survey, we will randomize participants to: ST vs. UC. Participants will complete a follow-up survey at 2-3-months post-randomization. Our primary outcome is genetic testing uptake.

Eligibility and Accrual. Men eligible for this study are currently being followed at MGUH or MWHC for either:

Metastatic prostate cancer;  
Gleason 7+ prostate cancer.

We will exclude patients who have had, or are already scheduled for genetic counseling or testing for *BRCA1* or *BRCA2* mutations. We will also exclude men who cannot participate in English and provide meaningful consent. We will recruit participants from medical and radiation oncology clinics at MGUH and MWHC. These clinics currently follow well over 1000 eligible patients.

Gender and Minorities. Participants will be adult men. Given the racial/ethnic breakdown of the clinics we are recruiting from. We expect that at least 30% of participants will be members of racial/ethnic minority groups.

Recruitment. Working with our clinical collaborators and the Survey, Recruitment and Biospecimen Collection Shared Resource (SRBSR) will obtain contact information of potentially eligible patients from clinical databases and/or the EMR. We will mail an introductory letter describing the study (from the study MPIs and the patient's physician), opt-out postcard/phone number, informed consent document and a print version of the baseline survey to all potentially eligible participants. We will also email electronic versions of these materials for patients who prefer to complete them online. Two-weeks following this mailing, an SRBSR research assistant (RA) will call patients who have neither opted out nor completed the baseline survey. For men who have not returned the consent document, we will use an IRB-approved verbal consent for completing the baseline survey and request return of the written consent prior to randomization. Following completion of print or electronic consent and the baseline survey, the RA will randomize participants. Men randomized to ST will be sent a priority mail packet with detailed genetic testing educational material. Men randomized to UC will be mailed a letter informing them that they meet guidelines for genetic counseling and provided with contact information to schedule a genetic counseling appointment with a LCCC genetic counselor.

Randomization. Following completion of the baseline survey and consent document, an RA will randomize participants via computer-generated random numbers in blocks of 8 and a ratio of 1:1. Participants will be notified of their random assignment via letter and email.

**Assessments.** We will administer baseline (T0) and 2- to 3-month (T1) follow-up telephone/electronic surveys. Genetic testing uptake will be assessed via clinical records and basic clinical and demographic information abstracted from the EMR. See Table 1 for assessment instruments and schedule of administration.

Table 1. Measures		T0	T1
Variables	Measures		
Covariates/Background Variables	Demographics, clinical variables, family history (EMR/survey)	X	
Health Literacy	Brief Health Literacy Screening Tool	X	
Genetic Test Uptake	Study Records		X
Knowledge/Risk Comprehension	Genetic Knowledge Scale and Perceived Mutation Risk.	X	X
Attitudes	Adapted version of the Multimodal Measure of Informed Choice (MMIC), Fatalism, Medical Mistrust Index	X	
Decision Regret	Decisional-Regret Scale.		X
Decision Satisfaction	Satisfaction with Decision Scale.		X
Distress	Cancer distress: PROMIS Anxiety and Depression; Genetic testing distress MICRA.	X	X
Quality of Life/Functional Status	PROMIS Physical Function and Social Function Short Forms	X	X
Cascade Testing	Number of relatives who have proceeded with genetic testing.		X

**Streamlined Testing (ST) Intervention.** Men randomized to ST will be sent a priority mail packet with the ST print education materials and information on how to proceed with genetic testing. ST participants will have the option of proceeding directly to genetic testing or scheduling a telephone genetic counseling session. The content of the ST intervention is described in section 5.0 above.

**Usual Care (UC).** After completion of the baseline survey, UC participants will be sent a letter from their physician indicating that they meet eligibility criteria for genetic testing, recommending that they schedule genetic counseling and providing a contact telephone number to schedule their session. Patients may opt for free telephone genetic counseling.

**Genetic Testing.** Participants who choose to pursue genetic testing will be offered a standard clinical multigene panel of at least 40 genes, including *BRCA* and genes associated with potential differential diagnoses (e.g., Lynch syndrome). All testing will be performed by Invitae, a CLIA certified clinical lab not affiliated with the GLCCC. Invitae offers genetic testing free of charge to eligible prostate cancer patients (all study participants will be eligible for free genetic testing through Invitae). Prior to proceeding with genetic testing, participants will be required to sign and return a clinical genetic testing consent form, after which we will mail them an at-home DNA kit for saliva collection which will be returned directly to Invitae (shipping costs are pre-paid).

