**10.0** **Inclusion and Exclusion Criteria\***

*10.1* Screening for Eligibility: The Survey, Recruitment and Biospecimen Collection Shared Resource (SRBSR) will work with our clinical collaborators to obtain a list of potentially eligible patients from the clinical databases and the EMR. To each potentially eligible patient, we will mail an introductory letter (from the study Principal Investigators and the patient's physician), opt-out postcard/phone number, informed consent document and baseline survey (we will also email electronic versions of these materials). Two-weeks following this mailing, we will call all patients who have not opted out or completed the baseline survey. At the start of this telephone call we will confirm study eligibility.

*10.2* Inclusion Criteria:

- Men who are being followed at MGUH or MWHC for metastatic prostate cancer or Gleason 7+ prostate cancer.

Exclusion Criteria:

- Above age 80.
- Previous cancer genetic counseling or currently scheduled for cancer genetic counseling related to the *BRCA1* or *BRCA2* genes.
- Have had or are scheduled for germline cancer genetic testing of the *BRCA1* or *BRCA2* genes.
- Cannot participate in English
- Are not capable of providing informed consent

*10.3* We will exclude adults unable to provide meaningful informed consent, individuals under the age of 18 and prisoners. Since the study focuses on prostate cancer survivors, women are ineligible.

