## **17.0 Data Management\* and Confidentiality**

*17.1* Data Analysis: We will characterize participants by comparing them to decliners on key demographic and clinical variables derived from the EMR. After performing univariate analysis on dependent variables, we will apply any needed normalizing or variance stabilizing transformations. We will follow Consort guidelines for Intent-to-Treat analyses (ITT). We will compare groups at baseline with  $\chi^2$  and t-tests and will include covariates that are associated with group ( $p < 0.10$ ) in our final models.

**Aim 1: Evaluate the impact of Proactive Streamlined Education and Testing (ST) vs. Usual Care (UC) on genetic testing.** Analysis: H1.1: Patients randomized to ST will be more likely to complete genetic testing compared to UC. We will use logistic regression to test this hypothesis. After entering significant covariates, we will add intervention arm to test the overall intervention effect. H1.2: Participants randomized to ST will make better informed genetic testing decisions (characterized by high knowledge, risk comprehension and positive attitudes) compared to UC. Using multiple regression, we will enter control/confounding variables and intervention to test the impact of group on our informed decision making outcomes (knowledge, testing attitudes, risk comprehension). H1.3: Few patients in the ST arm will opt for traditional genetic counseling prior to testing. We will conduct descriptive analyses describing the proportion of ST participants who opt for genetic counseling vs. proceed directly to testing vs. opt against testing.

**Aim 2: Evaluate patient satisfaction and psychosocial outcomes in ST vs. UC.** Analysis: H2.1: Compared to UC, those randomized to ST will be more satisfied with their genetic testing decision and will have less decisional regret. After identifying baseline confounders of each outcome, we will generate linear regression models in which we enter: 1) confounders; 2) genetic test result (dummy

coded to generate comparisons of carriers vs. non-carriers and non-carriers vs. untested); 3) group assignment. In the event that we have an insufficient number of PV carriers for these analyses, we will categorize test result into two levels (tested vs. untested) and evaluate results among PV carriers more descriptively. Results of Aim 2 analyses will be primarily focused on generating effect size estimates for our planned trial of newly diagnosed prostate cancer patients.

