**Aim 3: Evaluate the impact of ST vs. UC on uptake of cascade testing in unaffected family members.** In exploratory analyses designed to provide effect size estimates for our planned R01, we will use t-test to compare the ST to UC on the number of relatives of PV carriers who undergo cascade genetic testing.

**Power:** Power estimates are for 2-tailed tests ( $\alpha=.05$ ). The study is powered based on our primary outcome of patient genetic testing uptake. We expect no attrition since data will be abstracted from clinic records. With no relevant studies on which

Table 2. Sample Size Calculation			
	ST Uptake		
UC Uptake	.40	.45	.50
10%	39	25	20
15%	49	36	27
20%	81	54	39

to base our effect sizes for this pilot study, Table 2 displays the necessary sample size (per group) to obtain 80% power for a range of potential clinically significant effects on test uptake (40%-50% for ST; 10%-20% for UC). Based on this analysis, we will enroll 120 participants in order to attain 80% power to detect a clinically meaningful difference between 20% in UC and 45% in ST. For our secondary outcomes, a sample size of 120 and 10% attrition at 3-months (n=108 in final sample) will provide  $> 80\%$  power to detect medium sized effects of  $d=.54$  SDs on our secondary outcomes (e.g., decisional conflict, patient satisfaction). This effect size is well within the range that we have seen in previous studies and represents an effect that is generally considered to be clinically significant.

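### Disease group is neither a stratification factor nor a fixed term in the H1.1 model, so a chance imbalance can go unadjusted; the effect is small and the remedy nearly free

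*Combined protocol and SAP*

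**What the plan says.** Under Randomization in section 6.0, "an RA will randomize participants via computer-generated random numbers in blocks of 8 and a ratio of 1:1". No stratification factor is named.

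Section 10.2 admits "Men who are being followed at MGUH or MWHC for metastatic prostate cancer or Gleason 7+ prostate cancer", and no section sets a quota for either group. Sections 1.0 and 25.1 add family history or Ashkenazi Jewish ancestry as a condition for the Gleason 7+ route; sections 6.0 and 10.2 do not.

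Section 17.1 compares the arms at baseline and carries forward covariates associated with arm at p<0.10. For H1.1 it then says: "After entering significant covariates, we will add intervention arm to test the overall intervention effect". No estimate of uptake by disease group is planned. Table 1 lists clinical variables and family history at baseline, without naming disease group.

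The power paragraph of section 17.1 states that "we will enroll 120 participants in order to attain 80% power to detect a clinically meaningful difference between 20% in UC and 45% in ST". Section 2.0 describes the pilot as preparation for "a planned multisite R01 study of newly diagnosed patients with high risk localized or metastatic disease".

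**The concern.** The trial pools two groups of men who may have different reasons to be tested. Section 3.0 says "NCCN guidelines suggest germline testing in patients with castration resistant metastatic prostate cancer to guide the early use of platinum chemotherapy", whereas it describes testing in qualifying localised Gleason 7+ disease as something to be considered. Sections 2.0 and 3.0 also name low perceived relevance as a cause of low uptake. It is reasonable to infer that uptake could differ by disease group, although the plan never says so.

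If it does, two things follow. A chance difference between the arms in the share of metastatic men shifts the primary contrast, and the p<0.10 screen may not bring disease group into the model. Also, the planned R01 receives one pooled effect from a mix that the pilot does not fix.

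**Working it through.** **Inputs from the plan.** 120 men, 1:1, so 60 per arm; two-sided alpha 0.05; uptake 20% v 45%; no attrition for the primary outcome (section 17.1, Power); covariate screen at p<0.10 (section 17.1).

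**Assumptions, not in the plan.** Metastatic share 20–50%; uptake gap between disease groups 10–30 points.

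**1. The plan's own figure.** Pooled two-proportion formula, mean uptake 0.325:

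n = [1.960·√(2·0.325·0.675) + 0.842·√(0.20·0.80 + 0.45·0.55)]² / 0.25² = 53.9, so 54 per group. This matches Table 2. At 60 per arm, power is 84.1%.

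**2. Chance imbalance.** If M of the 120 men are metastatic, the number k in one arm of 60 is hypergeometric (120, M, 60). The gap in metastatic share is |2k − M|/60, with SD (2/60)·√[(M/4)(120 − M)/119]. For M = 36 the SD is (2/60)·√(9·84/119) = 8.4 points. Over the range it is 7.3 to 9.2 points.

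**3. What the p<0.10 screen catches.** Uncorrected chi-square, threshold 2.706. For M = 36:

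- 21:15 (10.0 points): 120·(21·45 − 39·15)²/(60·60·36·84) = 1.43, not flagged.
- 22:14 (13.3 points): 2.54, not flagged.
- 23:13 (16.7 points): 3.97, flagged.

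| Metastatic men | P(gap ≥ 10 points) | First gap flagged | Share of those gaps missed |
|---|---|---|---|
| 24 | 25% | 13.3 | 57% |
| 25 | 18% | 15.0 | 60% |
| 35 | 23% | 15.0 | 53% |
| 36 | 32% | 16.7 | 77% |
| 48 | 35% | 16.7 | 74% |
| 59 | 27% | 18.3 | 75% |
| 60 | 36% | 16.7 | 72% |

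Even totals give higher probabilities because a gap of exactly 10 points is then possible and is counted. Simulating blocks of 8 with a random metastatic total (10,000 runs) gives 27% at a 30% share and 32% at a 50% share. With stratified blocks no run reached 10 points; the largest gap was about 6.

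**4. Effect on the primary contrast.** Shift = imbalance × uptake gap between disease groups: 0.10 × 0.10 = 1 point, up to 0.10 × 0.30 = 3 points. The planned difference is 25 points, with standard error √[(0.16 + 0.2475)/60] = 8.2 points.

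**5. Power.** Simulated logistic regression, 50% metastatic, 20% v 45% overall, 8,000 runs per setting:

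| Uptake gap between groups | Unadjusted | p<0.10 rule | Stratified, term kept |
|---|---|---|---|
| 15 points | 84.0% | 84.0% | 85.6% |
| 30 points | 83.9% | 84.7% | 88.4% |

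A repeat with 6,000 runs (simulation error about 0.5 points) gave 85.5% and 88.7% in the last column, hence 86–89%. In that repeat, keeping the term without stratified lists gave 84.4% and 88.3%, against 83.5% and 83.7% unadjusted. So roughly half or more of the gain comes from the covariate: about 0.8 of 2.0 points at the smaller gap, where simulation error is large relative to the gain, and 4.5 of 4.9 at the larger.

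**6. Estimates within disease group.** The 95% half-width at 20% v 45% is 1.96·√(0.4075/n): ±23 points at 30 per arm and ±36 at 12, against ±16 pooled. With 30 per arm in both groups, the difference between the two group effects has half-width 1.96·√(2·0.4075/30) = 32 points.

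**7. Dependence on the mix.** If the true effects were 15 and 35 points (assumed), the pooled effect would be 15s + 35(1 − s), where s is the share of the lower-effect group: 31 points at s = 0.2 and 19 at s = 0.8.

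**The case against.** The case against has real force, and most of it stands.

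- **No document says that uptake differs by disease group.** Section 2.0 recommends testing for metastatic and qualifying Gleason 7+ men in the same sentence. The barriers in sections 2.0 and 3.0 are not tied to stage, and testing is free to all participants. The uptake gaps used here are assumptions.
- **Unstratified blocked allocation is valid.** A reader might infer that the primary comparison is biased. It is not: the imbalance is chance, the ordinary standard error already allows for it, and a shift of 1–3 points is small beside 8.2.
- **The screen does catch large imbalances.** With 24 metastatic men, a 16:8 split has an 11% chance of arising or being exceeded. It gives p = 0.068 and would be flagged, provided disease group is among the variables compared.
- **Much of the power gain needs no change to the lists.** Keeping the covariate supplies roughly half or more of it.
- **The data are not lost.** Clinical variables are collected at baseline and uptake comes from records, so a table by disease group could be produced later.

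What does not stand is that the p<0.10 rule closes the gap. It selects on association with arm, not with outcome; it does not name disease group; and it leaves more than half of the 10-point imbalances unadjusted.

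**Conclusion.** This is a cheap improvement of low to moderate priority, not an error. The plan leaves a plausible predictor of uptake to chance and to a screen that usually misses a 10-point imbalance. On an assumed metastatic share of 20–50%, such an imbalance arises in about 18–36% of trials and goes unadjusted in about 53–77% of those. At assumed uptake gaps of 10–30 points it moves the result by about 1–3 points out of 25.

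Two stronger readings should be resisted. One is that the sample size is affected: the 54 per group reproduces, and 120 men give 84.1% power without any of this. The other is that the R01 will be mis-sized because the pilot reports only a pooled effect. That requires effects that differ by disease group and a different mix in the R01, and the documents give neither. The R01 also enrols newly diagnosed men rather than men in follow-up, a difference that matching the disease mix would not remove. Within-group estimates from this pilot would be too imprecise for subgroup tests or for reliable re-weighting on their own.

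**What to change.** 1. **Section 6.0, Randomization.** Generate separate 1:1 permuted-block lists for metastatic and non-metastatic men. Define non-metastatic as Gleason 7+ without metastases, because the eligibility routes overlap: a man with metastatic disease can also be Gleason 7+.
2. **Section 17.1, H1.1.** Keep disease group in the logistic model whatever its baseline p-value. If the lists are not changed, pre-specify this covariate alone.
3. **Section 17.1, reporting.** Give uptake by arm, with the risk difference and 95% CI, within each disease group, labelled as descriptive estimates for the R01.
4. **Eligibility text.** Reconcile the Gleason 7+ criterion in sections 1.0 and 25.1 with that in sections 6.0 and 10.2, so that the non-metastatic stratum is clearly defined.

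The cost is two computer lists instead of one, a few lines of analysis text and one table, with no extra patients or data. Disease group must be confirmed before allocation. Incomplete last blocks can leave the arms uneven by a few men (at most 4 per list with blocks of 8).
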